### 3. OBJECTIVES AND ENDPOINTS

[Table 4](#) presents the objectives and endpoints.

**Table 4: Objectives and Endpoints**

Objectives	Endpoints
Primary	
To evaluate the safety and tolerability of INCB099280 in combination with axitinib (Part 1).	
 
• Occurrence of DLTs.
 
• Incidence of TEAEs, including assessment of physical examinations, changes in vital signs and ECGs, and analysis of clinical laboratory samples.
 
• Incidence of TEAEs leading to a dosing modification (treatment interruption, dose reduction, and permanent discontinuation of either study drug).
 

To assess the antitumor activity of INCB099280 in combination with axitinib (Part 2).	Objective response, defined as the best overall response of CR or PR by investigator assessment per RECIST v1.1.
Secondary	
To evaluate the safety and tolerability of INCB099280 in combination with axitinib (Part 2).	
 
• Incidence of TEAEs, including assessment of physical examinations, changes in vital signs and ECGs, and analysis of clinical laboratory samples.
 
• Incidence of TEAEs leading to a dosing modification (treatment interruption, dose reduction, and permanent discontinuation of either study drug).
 

To assess the antitumor activity of INCB099280 in combination with axitinib.	
 
• Objective response (Part 1), defined as the best overall response of CR or PR by investigator assessment per RECIST v1.1.
 
• Disease control, defined as the best overall response of CR, PR, or SD by investigator assessment per RECIST v1.1.
 
• DOR, defined as the time from the first CR or PR until disease progression by investigator assessment per RECIST v1.1 or death from any cause, whichever occurs earlier.
 

**Table 4: Objectives and Endpoints (Continued)**

Objectives	Endpoints
Secondary (continued)	
To characterize the PK profile of INCB099280 when administered in combination with axitinib.	
 
• INCB099280 and axitinib plasma concentrations.
 
• INCB099280 PK parameters by NCA methods such as <math>C_{max}</math>, <math>t_{max}</math>, <math>AUC_{0-4h}</math>, <math>C_{max,ss}</math>, <math>t_{max,ss}</math>, <math>AUC_{0-12h}</math>, <math>C_{avg}</math>, <math>C_{tau}</math>, <math>t_{1/2}</math>, <math>CL_{ss}/F</math>, and <math>V_z/F</math>.
 

## 4. STUDY DESIGN

### 4.1. Overall Design

This is an open-label, multicenter study performed to evaluate the safety, tolerability, antitumor activity, and PK and pharmacodynamic effects of INCB099280 in combination with axitinib in adults with previously treated advanced clear cell ovarian cancer, rare histological subtype epithelial cancer of the gynecological tract, endometrial cancer, or cervical cancer who have received at least 1 prior line of systemic chemotherapy and are not candidates for curative surgery or (chemo)radiation. The study will be composed of a dose-finding part and a dose-expansion part. See [Table 2](#) for the key study design elements and [Figure 1](#) for the study design schema.

INCB099280 and axitinib will be administered orally BID, either with a [REDACTED] meal or after the participant has [REDACTED] for at least [REDACTED] hours, on a continuous daily dose administration schedule. If a participant is unable to tolerate combination treatment, they will have met the criterion for study treatment discontinuation. However, on a case-by-case basis, after discussion between the medical monitor and the investigator, a decision may be made to continue INCB099280 monotherapy. The planned treatment duration for INCB099280 is 2 years (ie, up to 35 treatment cycles of 21 days), calculated from the first dose of study treatment.

Participants will be monitored closely for AEs from the time they have given written informed consent until 90 days after the end of treatment or until the initiation of a subsequent systemic

therapy, whichever occurs earlier. Adverse events will be assessed for their severity (graded according to the NCI CTCAE v5.0), seriousness, suspected relatedness to the study medication, action taken with regard to the study treatment and whether they fulfill a DLT criterion, and potential immune-mediated etiology. In the event of toxicity, study treatment may be adjusted by dosing interruptions with or without dose reductions of axitinib on resumption of treatment (see Section 6.6).

Even though INCB099280 and axitinib are metabolized primarily in the liver by [REDACTED], a clinically significant PK interaction is not anticipated. However, PK assessments will be conducted in this study to identify any effect of the combination on INCB099280.

Antitumor activity will be assessed per RECIST v1.1. Tumor assessments will be performed at baseline, 6 and 12 weeks after the start of treatment, and Q12W thereafter until disease progression or the participant has completed 2 years of treatment.

The study assessments and procedures, including the SoA, are outlined in Table 3.

#### 4.1.1. Part 1: Dose Finding

Participants with diagnoses as defined for all disease-specific cohorts may be enrolled in Part 1. During the dose-finding part of the study, up to 2 doses of axitinib administered in combination with INCB099280 will be evaluated to identify a dose for further evaluation in the dose-expansion phase of the study.

The starting doses (Dose Level 1) are INCB099280 400 mg BID and axitinib 5 mg BID (see Section 2.3 and Section 2.4.2 for further details). Up to approximately 12 participants will be enrolled in this part of the study.

Dose levels, based on Dose Level 1 tolerability, are illustrated in Figure 4.

Dose Level –1 will only be investigated if a dose de-escalation rule is met at Dose Level 1 (see Section 6.5.2).

[figure not shown]
Decisions on dose will be based on DLTs observed in participants during the first 3 weeks of treatment (see Section 6.5).

No intraparticipant dose escalation of either of the study drugs will be permitted.

Dose finding may conclude after one of the following:

1. At least 9 DLT-evaluable participants have been enrolled in a dose level and with a hybrid design decision rule of "stay" met (see Table 5); then the highest dose with an observed DLT rate no higher than the target toxicity rate of 30% will be treated as the preliminary MTD.
2. At least 3 DLT-evaluable participants have been enrolled in Dose Level 1 and with a hybrid design decision rule of "escalate" met (see Table 5); then Dose Level 1 is considered safe and tolerable, and the MTD has not been reached.
3. At least 3 DLT-evaluable participants have been enrolled in Dose Level –1 and with a hybrid design decision rule of either "de-escalate" or "eliminate" met (see Table 5); then none of the dose levels will be considered safe and tolerable.

**Figure 4: Dose Levels in the Dose-Finding Part of the Study**

**Table 5: Decision Rules of the Hybrid Design With a 30% Target Toxicity Rate**

Participants With at Least 1 DLT	Number of Participants Evaluable for DLT												
	3	4	5	6	7	8	9	10	11	12	13	14	15
0	E	E	E	E	E	E	E	E	E	E	E	E	E
1	S	S	S	E	E	E	E	E	E	E	E	E	E
2	D	D	S	S	S	S	S	S	E	E	E	E	E
3	DU	DU	D	D	S	S	S	S	S	S	S	S	S
4		DU	DU	DU	D	D	D	S	S	S	S	S	S
5			DU	DU	DU	DU	DU	D	D	D	S	S	S
6				DU	DU	DU	DU	DU	DU	D	D	D	S
7					DU	DU	DU	DU	DU	DU	DU	D	D
8						DU	DU	DU	DU	DU	DU	DU	DU
9							DU	DU	DU	DU	DU	DU	DU

D = de-escalate to the next lower dose; DU = the current dose is unacceptably toxic; E = escalate to the next higher dose; S = stay at the current dose.

Note: The decision rules are modified from mTPI design of a target DLT rate  $p_T$  of 30% and a dose-exclusion cutoff of 0.95 to further control the overdosing toxicity using the posterior probability of the DLT rate in the overdosing interval (0.33, 1) of  $< 0.75$ . Flat noninformative prior Beta(1,1) is used as a prior and  $\varepsilon_1 = \varepsilon_2 = 0.03$  (Ji et al 2010, Ji et al 2013).

On completion of the dose finding in Part 1, a dose will be selected for further evaluation and optimization in disease-specific expansion cohorts in Part 2 of the study (see Section 4.1.2). The selection of a dose to be evaluated in Part 2 will be based on the collective data available from the dose-finding part of the study, including dose/exposure-response analyses for safety, antitumor activity, and pharmacodynamic activity. The RDE selected for evaluation in Part 2 will not exceed the MTD. These expansion cohorts are intended to further evaluate the safety and tolerability beyond the initial dose-finding part of the study, assess preliminary antitumor activity, accumulate data on exposure and pharmacodynamic activity, and further characterize the dose- and exposure-response relationships of this combination regimen.

#### **4.1.2. Part 2: Dose Expansion**

On completion of Part 1, adult participants with recurrent, locally advanced, unresectable or metastatic cancer with the following histologies will be enrolled in 1 of 4 disease-specific cohorts:

- Cohort 1: Clear cell ovarian cancer (including primary peritoneal and fallopian tube) with at least 50% clear cell histology
- Cohort 2: Other rare histological subtype epithelial cancer of the gynecological tract, including but not limited to carcinosarcoma, neuroendocrine tumors of low and high grade (including small cell carcinoma), ovarian mucinous adenocarcinoma, low-grade ovarian serous carcinoma, SCCOHT, squamous cell cancer (excluding cervical and endometrial), and vulvar or vaginal cancer, regardless of histological subtype
- Cohort 3: Endometrial cancer (including clear cell histology)  
Note: This cohort excludes endometrial carcinosarcoma (malignant mixed Müllerian tumor), endometrial leiomyosarcoma, and endometrial stromal sarcoma.
- Cohort 4: Cervical cancer, including squamous, adenosquamous, or adenocarcinoma (inclusive of clear cell histology).

Up to 30 participants will be enrolled in each of the 4 disease-specific cohorts.

Clinical activity and safety will be monitored (see Section 4.1.3 and Section 8) to ensure participant safety and that clinical benefit is seen. Throughout Part 2 of the study, continuous monitoring will occur to ensure that futility is not met. At each interim monitoring of the study, all observed data will be taken into consideration and Bayesian predictive probabilities will guide decisions on future enrollment (see Section 10.5).

#### **4.1.3. Safety Monitoring**

During the conduct of Part 1 of the study, the sponsor will convene approximately biweekly telephone conferences with the investigative site staff to provide clinical updates on participants who remain on-study. Investigators who are unable to attend and have participants on-study will be requested to provide written updates prior to the meeting to keep all involved parties informed. An agenda will be provided in advance of these meetings, and minutes (including written summaries of cumulative participant-level safety and tolerability information, antitumor activity, and key discussion points and decisions) will be circulated to all investigative sites.

During Part 2 of the study, the sponsor monitoring of the study will include periodic DMC review. If any issues concerning participant safety arise during the study, this will be discussed at the investigator-sponsor meetings and, if appropriate, will be referred to the DMC.

Enrollment of participants into Part 2 may be suspended if > 40% of participants (when 5 or more participants have been enrolled) have an AE  $\geq$  Grade 3 that is attributable to the investigational agent (INCB099280) and that persists over 7 days despite adequate management.

See Section 5.7 for additional information on the Part 2 DMC.

## 4.2. Overall Study Duration

The study begins when the first participant signs the study ICF. The end of the study is defined as the date of the last scheduled procedure shown in the SoA (see [Table 3](#)) for the last participant in the study globally.

A participant is considered to have completed the study if they have completed all parts of the study, including the last scheduled procedure shown in [Table 3](#). The study is considered completed when the last participant completes the last scheduled procedures shown in the SoA, withdraws from the study, or is lost to follow-up.

In the European Union/European Economic Area, the results of the study will be based on the date of the last scheduled procedure shown in [Table 3](#) of the last participant in the study globally to ensure the results are robust, meaningful, and representative of all multiregions by having complete follow-up data determined by the statistical hypotheses for the objectives established. Not using the global date could potentially jeopardize the integrity of the study and invalidate the study conclusions due to potential bias, thus potentially violating the statistical analysis assumptions.

The study will include a 28-day screening period during which eligibility will be assessed, continuous combination treatment in consecutive 21-day cycles as long as participants are receiving benefit and have not met any criteria for study withdrawal, a safety follow-up period of 30 (+ 7) days and 90 (+ 14) days after EOT, and disease status follow-up Q12W ( $\pm$  14 days) after EOT for participants who discontinue for reasons other than PD. The planned treatment duration with INCB099280 is up to 2 years.

If there are  $\leq 3$  participants on study treatment for more than 6 months, a database lock of the study may occur to allow for the analysis of the study data. Any remaining participants may continue to receive study treatment, to be seen by the investigator, and to have study assessments and procedures conducted as per usual standard of care for this population. The investigator will be expected to monitor for and report any AEs leading to study drug discontinuation, SAEs, pregnancies, and deaths as detailed in [Section 9](#). The remaining participants are considered to be on-study until a discontinuation criterion is met and written notification is provided to the sponsor.

## 4.3. Study Termination

The investigator retains the right to terminate study participation at any time, according to the terms specified in the study site contract. The investigator is to notify the IRB/IEC of the study's completion or early termination in writing, send a copy of the notification to the sponsor or sponsor's designee, and retain 1 copy for the site study regulatory file.

The sponsor may terminate the study electively if, for example, required by regulatory decision or upon advice of the DMC. If the study is terminated prematurely, the sponsor will notify the investigators, the IRBs and IECs, and the regulatory bodies of the decision and reason for termination of the study. The DMC will recommend termination of the study if warranted, as described in [Section 5.7](#).

## 5. STUDY POPULATION

Deviations from eligibility criteria are not allowed because they can potentially jeopardize the scientific integrity of the study, regulatory acceptability, and/or participant safety. Therefore, adherence to the criteria as specified in this Protocol is essential. Prospective approval of Protocol deviations to recruitment and enrollment criteria, also known as Protocol waivers or exemptions, are not permitted.

### 5.1. Inclusion Criteria

Participants are eligible to be included in the study only if all of the following criteria apply:

1. Able to understand and willing to sign a written ICF for the study.
2. Age  $\geq 18$  years at the time of signing of the ICF.
3. Recurrent, locally advanced, unresectable or metastatic cancer with the following histologies:
  - a. Cohort 1: Clear cell ovarian cancer (including primary peritoneal and fallopian tube); tumor specimens must be at least 50% clear cell histology as determined by the named specialist gynecological histopathologist(s) reviewing this on behalf of the study site
  - b. Cohort 2: Other rare histological subtype epithelial cancer of the gynecological tract, including but not limited to carcinosarcoma, neuroendocrine tumors of low and high grade (including small cell carcinoma), ovarian mucinous adenocarcinoma, low-grade ovarian serous carcinoma, SCCOHT, squamous cell cancer (excluding cervical and endometrial), and vulvar or vaginal cancer, regardless of histological subtype
  - c. Cohort 3: Endometrial cancer (including clear cell histology)  
  
Note: This cohort excludes endometrial carcinosarcoma (malignant mixed Müllerian tumor), endometrial leiomyosarcoma, and endometrial stromal sarcoma.
  - d. Cohort 4: Cervical cancer, including squamous, adenosquamous, or adenocarcinoma histologies (including clear cell histology)
4. Disease progression on or after at least 1 prior systemic line of chemotherapy for gynecological cancer:
  - For Cohorts 1 and 2, participants must have received  $\geq 1$  but  $\leq 3$  prior lines of systemic chemotherapy for gynecological cancer. Prior anti-PD-(L)1 therapy is permitted.
  - For Cohorts 3 and 4, participants must have received  $\leq 2$  prior lines of systemic therapy, which may include prior platinum-based chemotherapy. Participants must have received prior anti-PD-(L)1 therapy ( $\geq 6$  months on therapy without progression).

Note: Endocrine therapy is not counted as a prior line of therapy.

5. Advanced disease not amenable to curative surgery or (chemo)radiation.

6. At least 1 measurable lesion based on radiographic imaging per RECIST v1.1. The measurable lesion should be outside any prior radiation field unless progression occurred at that site.

Note: If participants have only 1 measurable lesion per RECIST v1.1, the biopsy specimen must be obtained from a nontarget lesion or archival tissue.

7. Willing to provide tumor tissue (fresh or archival). Formalin-fixed, paraffin embedded tissue blocks are preferred to slides.
  - Up to 15 participants in Cohort 1 and up to 15 participants in Cohort 2 must be willing to provide fresh biopsy specimens at screening, 6 to 8 weeks after the start of treatment, and at the time of disease progression/EOT (if technically feasible and safe).
8. ECOG performance status score of 0 or 1.
9. Life expectancy > 3 months, in the opinion of the investigator.
10. Willing and able to comply with all Protocol requirements, including all scheduled visits, Protocol procedures, and the ability to swallow oral medication.
11. Willingness to avoid pregnancy based on the criteria below.
  - a. Women of childbearing potential must:
    - Have a negative serum pregnancy test at screening and must agree to take appropriate precautions to avoid pregnancy (with at least 99% certainty) from screening through 190 days after the last dose of study treatment. Permitted methods that are at least 99% effective in preventing pregnancy (see [Appendix A](#)) should be communicated to the participants and their understanding confirmed.
    - Refrain from donating oocytes from screening through 190 days after the last dose of study treatment.
  - b. Women of nonchildbearing potential (ie, surgically sterile with a hysterectomy and/or bilateral oophorectomy OR  $\geq 12$  months of amenorrhea and at least 50 years of age) are eligible.

## 5.2. Exclusion Criteria

Participants are excluded from the study if any of the following criteria apply:

### Cancer History

1. Known additional malignancy that progressed or required treatment during the past 3 years.

Note: Exceptions include adequately treated basal cell carcinoma, cutaneous SCC, superficial (nonmuscle invasive) bladder cancer, and noninvasive cancers (eg, ductal carcinoma in situ, lobular carcinoma in situ, or in situ cervical cancer).

2. Known leptomeningeal disease.

3. Known CNS metastases as follows:
  - a. Participants with untreated CNS metastases.
  - b. Participants with treated CNS metastases who have disease progression, are clinically unstable within 2 weeks of the initiation of study treatment, or require increasing doses of steroids and/or a steroid dose of more than 1 mg of dexamethasone daily (or equivalent).

### **Prior Cancer Therapy**

4. Removed during Protocol Amendment 1.
5. Prior therapy with antiangiogenic small-molecule TKIs targeting the VEGF pathway.  
Note: Prior treatment with anti-VEGF therapy (eg, bevacizumab, aflibercept) is allowed.
6. Treatment with anticancer therapies or investigational drugs within the following intervals before the first administration of study treatment:
  - a. At least 14 days for chemotherapy or targeted small-molecule therapy
  - b. At least 28 days for a prior monoclonal antibody used for anticancer therapy (including anti-PD-1 antibodies)
  - c. At least 5 half-lives from receipt of prior anti-PD-L1 therapy  
Note: atezolizumab:  $\geq 19$  weeks; durvalumab:  $\geq 15$  weeks; avelumab:  $\geq 30$  days.
  - d. At least 28 days or 5 half-lives (whichever is longer) for investigational study drugs or devices
7. Toxicity from prior therapy that has not recovered to  $\leq$  Grade 1 or baseline.  
Exceptions: Anemia that is not transfusion-dependent and any grade alopecia.
8. Radiation therapy within 2 weeks of the first dose of study treatment.  
Note: Participants must have recovered from all radiation-related toxicities to  $\leq$  Grade 1 and not require corticosteroids.
9. Participation in an interventional clinical study while receiving study treatment.

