### **Medical History**

10. History of any of the following cardiovascular conditions within 12 months of the initiation of study treatment:
  - a. Symptomatic ischemic heart disease or unstable angina pectoris
  - b. Myocardial infarction
  - c. Cardiac angioplasty or stenting
  - d. Coronary or peripheral artery bypass graft
  - e. Class III or IV heart failure per NYHA (see [Appendix D](#))
  - f. Cerebrovascular accident or transient ischemic attack
11. Inadequately controlled hypertension (defined as SBP  $\geq 150$  mm Hg and/or DBP  $\geq 90$  mm Hg) based on an average of 3 BP readings at least 2 minutes apart.  
Note: Treatment with antihypertensive medication is allowed during screening to achieve BP with SBP/DBP  $< 150/90$  mm Hg.

12. History of hypertensive crisis or hypertensive encephalopathy.
13. Significant vascular disease (eg, aortic aneurysm requiring surgical repair or recent peripheral arterial thrombosis) within 6 months prior to initiation of study treatment.
14. History of deep vein thrombosis or pulmonary embolism within 6 months of screening.
15. History of thromboembolism while on anticoagulation therapy.
16. Active bleeding disorder or other history of clinically significant (non-GI) bleeding episodes within 30 days of enrollment.
17. History of hemoptysis (> 2.5 mL/1 teaspoon of bright red blood per episode) within 6 weeks prior to the initiation of study treatment.
18. Tumor known to invade or encase a major blood vessel.
19. Major surgical procedure within 1 month prior to initiation of study treatment or expected need for a major surgical procedure during the study.
20. Core biopsy or other minor surgical procedure, excluding placement of a vascular access device, within 3 days prior to the initiation of study treatment.
21. Clinically significant nonhealing wound, wound dehiscence, or active ulceration or untreated bone fracture.
22. History of interstitial lung disease, including noninfectious pneumonitis requiring steroids.
23. Clinically significant GI abnormality, including the following:
  - Inability to take oral medication
  - Requirement for enteral or parenteral nutrition
  - Conditions that may affect drug absorption, as well as those that interfere with GI transit, including gastric bypass surgery, gastric sleeve, or gastric band
  - Endoscopically determined active gastroduodenal ulcer(s)

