## Diagnostic Assessments

39. Clinically significant and uncontrolled arrhythmia.
40. An average QTcF interval  $> 480$  milliseconds on a triplicate ECG.
41. Left ventricular systolic dysfunction with an LVEF  $< 50\%$ .

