## Other Exclusions

42. Pregnant, expecting to conceive, or breastfeeding from consent until 190 days after the last dose of study treatment.
43. History or current evidence of a medical condition, therapy, or laboratory abnormality that, in the opinion of the investigator, might interfere with full participation in the study, increase the risk associated with study participation or the administration of the study medication, confound the results of the study, or make it inappropriate for the participant to take part in this study.
44. The following participants are excluded in France: vulnerable populations according to article L.1121-6 of the French Public Health Code and adults under legal protection, or who are unable to express their consent per article L.1121-8 of the French Public Health Code, not affiliated to a social security per article L.1121-8-1 of the French Public Health Code.

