**Table 11: Management Guidelines for Immune-Related Adverse Events (Continued)**

Severity (CTCAE v5 Grade)	INCB099280	Evaluation and Management
Hepatitis (AST/ALT increased and/or total bilirubin increased) (continued)		
Grade 2	Withhold INCB099280 until improvement to $\leq$ Grade 1.	
 
Repeat laboratory measurements every 3 days until return to baseline.
 
If elevations persist after 3 days or symptomatic, administer systemic corticosteroids (prednisone 0.5-1 mg/kg or equivalent) with taper over at least 1 month when symptoms improve to <math>\leq</math> Grade 1.
 
If inadequate improvement over 3 days, consider adding mycophenolate mofetil if an infectious cause is ruled out.
 
Infliximab should NOT be used.
 

Grade 3	Permanently discontinue INCB099280.	
 
Repeat laboratory measurements every 1-2 days until return to baseline.
 
Administer IV methylprednisolone 1-2 mg/kg or equivalent with taper around 4-6 weeks when <math>\leq</math> Grade 1 with re-escalation as needed.
 
If corticosteroid refractory, consider liver biopsy and addition of azathioprine or mycophenolate mofetil.
 
Infliximab should NOT be used.
 
Consultation with a hepatology specialist for additional workup as appropriate.
 

Grade 4	Permanently discontinue INCB099280.	
 
Recommendations as above for Grade 3.
 
2 mg/kg/d methylprednisolone or equivalent.
 

Dermatitis		
Grade 1	Continue INCB099280.	Treat with topical emollients and/or mild- to moderate-potency topical steroids.
Grade 2	Consider holding INCB099280.	
 
Monitor weekly for improvement. If no improvement after 4 weeks, regrade toxicity as Grade 3.
 
Supportive care with topical emollients, oral antihistamines, and medium- to high-potency topical steroids.
 
Consider initiating prednisone 0.5-1 mg/kg or equivalent followed by tapering over 4 weeks. For participants with pruritus without rash, consider topical anti-itch remedies.
 

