**Table 11: Management Guidelines for Immune-Related Adverse Events (Continued)**

Severity (CTCAE v5 Grade)	INCB099280	Evaluation and Management
Myocarditis or pericarditis (continued)		
Grade 2, Grade 3, and Grade 4 as well as biopsy-proven immune-mediated myocarditis, pericarditis (all grades)	Permanently discontinue INCB099280.	
 
Intensive care monitoring is strongly recommended.
 
Promptly start IV methylprednisolone (consider methylprednisolone pulse dosing [1 g/day for 3-5 days]); treat until cardiac function returns to baseline and then dose taper over 4-6 weeks.
 
If no improvement is noted within 24 hours on steroids, consider adding immunosuppressive agents (such as infliximab, antithymocyte globulin, and mycophenolate mofetil).
 
It is important to rule out sepsis and refer to the infliximab label for general guidance before using infliximab; infliximab is contraindicated in participants who have heart failure.
 

Nervous system disorders		
Grade 1	Continue INCB099280, or may withhold and monitor. Note: The following conditions require a hold of INCB099280: 
 
Aseptic meningitis
 
Encephalitis
 
	
 
Consultation with a neurology specialist is advised.
 
Monitor closely for any symptom progression.
 
Exclude alternative etiologies, empiric treatment as indicated.
 

Grade 2	Withhold INCB099280 until improvement to $\leq$ Grade 1. Note: Demyelinating diseases require INCB099280 to be stopped; may resume in consultation with neurology.	
 
Consultation with a neurology specialist advised and workup including MRI. Consider EMG, lumbar puncture, and CSF analysis.
 
Administer supportive care and corticosteroids.
 
Monitor closely for any symptom progression.
 
Workup for alternative etiologies, empiric treatment as indicated.
 

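### Prior anti-PD-(L)1 therapy is required or permitted, but no exclusion names a past severe immune-related event outside the lung, chiefly myocarditis or Grade 3-4 hepatitis

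*Protocol*

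**What the plan says.** **Entry.** Protocol 5.1, criterion 4, states for Cohorts 3 and 4: "Participants must have received prior anti-PD-(L)1 therapy", with at least 6 months on it without progression. For Cohorts 1 and 2 it states: "Prior anti-PD-(L)1 therapy is permitted". Neither sentence asks how that therapy was tolerated.

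**Exclusions in 5.2 that could bear on a past immune-related event.**
- Criterion 7: "Toxicity from prior therapy that has not recovered to" Grade 1 or baseline.
- Criterion 22: "History of interstitial lung disease, including noninfectious pneumonitis requiring steroids".
- Criterion 24: autoimmune disease treated systemically within 5 years.
- Criterion 41: "Left ventricular systolic dysfunction with an LVEF" below 50%.
- Criterion 43: a history that, in the investigator's opinion, might "increase the risk associated with study participation or the administration of the study medication".

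**On study.** In Table 11 the action for myocarditis or pericarditis of Grade 2 to 4, or of any grade when proven by biopsy, is "Permanently discontinue INCB099280". The same action is given for hepatitis of Grade 3 and of Grade 4. No alternative is listed in those rows.

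**The concern.** The protocol brings in patients who have already received the drug class, and in two of the four cohorts it insists on it. It then gives the class again, combined with a VEGFR inhibitor. Some of these patients may have had a serious immune-related event the first time. For the lung, the protocol treats such a history as a bar to entry even after recovery. For the heart and the liver it does not.

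The protocol's own background makes these two organs hard to pass over. Section 2.3.2 reports that, of 429 participants given axitinib with pembrolizumab, 4 (0.9%) died of treatment-related events. One death was from myocarditis and one from pneumonitis. The same section says Grade 3 or 4 liver enzyme elevations were more frequent with the combination than with either drug alone.

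At stake is the safety of individual patients. A woman could be re-exposed to a class that has already caused an event after which this protocol's guidance would take her off INCB099280 for good. Whether she is enrolled would depend on how each site exercises its judgment.

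**Working it through.** The protocol gives no figure to reproduce. The check takes two hypothetical patients through the exclusions. Patient A had Grade 3 immune myocarditis on an earlier anti-PD-1 antibody, has recovered, and has an LVEF of at least 50%. Patient B had Grade 3 immune hepatitis, now resolved. Both are off steroids and past the washout.

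| Exclusion (5.2) | What it tests | A | B |
|---|---|---|---|
| 6, washout | Time since prior therapy | passes | passes |
| 7, prior toxicity | Recovery to Grade 1 or baseline | passes | passes |
| 10, cardiac history | Ischemia, infarction, revascularization, NYHA III/IV failure, stroke or TIA within 12 months; myocarditis is not listed | passes, unless she had class III/IV failure in that window | passes |
| 22, lung history | Interstitial lung disease or pneumonitis | passes | passes |
| 24, autoimmune disease | Systemic treatment in the past 5 years | unclear | unclear |
| 33, immunosuppression | Use within the last 14 days | passes | passes |
| 38 (Table 6), liver tests | Screening ALT, AST, bilirubin | passes | passes |
| 41, LVEF | Current function | passes | passes |
| 43, general | Investigator's opinion | discretionary | discretionary |

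Two rows need comment.

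- **Exclusion 24.** It names autoimmune disease and does not mention immune-related adverse events. Section 6.6.5 lists autoimmune causes among those to be ruled out before an event is called immune-related, so the protocol treats the two as different. A site might still read a steroid-treated hepatitis into criterion 24, but the text does not oblige it to.
- **Exclusion 43.** Its words reach such a history, but only through the investigator's opinion, so two sites can decide the same case differently.

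Grade 4 immune colitis is a less clear example, because exclusion 23 gives inflammatory bowel disease and ulcerative colitis as perforation risks.

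**Comparison with Table 11.** Patient A's event falls in the myocarditis row and patient B's in the hepatitis row, and in both rows permanent discontinuation is the only action. Grade 3-4 pneumonitis carries the same action, and steroid-requiring pneumonitis is also excluded by history. The heart and liver events have no matching entry rule.

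**Exposed population.** Part 2: 4 × 30 = 120. Cohorts 3 and 4: 2 × 30 = 60, all pre-treated. Cohorts 1 and 2: 2 × 30 = 60, pre-treatment optional and its frequency not stated. Part 1 (up to about 12) draws on all four cohorts. These are ceilings on who is or may be pre-treated, not counts of patients with a relevant history.

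**The case against.** The strongest reply is that exclusion 43 already covers this. A past checkpoint-inhibitor myocarditis plainly can raise the risk of the study drug, and few investigators would judge otherwise. An entry rule and an on-study stopping rule may also legitimately differ. Both points stand in part: nothing is stated wrongly, and what remains is a choice between a named rule and judgment. But for steroid-requiring pneumonitis the protocol preferred a named rule, and it gives no reason for treating the heart and liver differently.

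Second, Section 6.6.5 introduces Table 11 as suggested measures and asks for discussion with the medical monitor. Section 6.6.7 makes stopping mandatory for events that meet the tables' criteria, but it points back to those tables. So Table 11 is best read as guidance that offers one option for these events.

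Third, the 6-month rule in Cohorts 3 and 4 will remove many early events. It does not exclude later ones, and Cohorts 1 and 2 have no such rule.

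Fourth, Section 2.4.2 argues for checkpoint-inhibitor rechallenge and cites tolerable safety. That argument is about recurrence after progression and does not address re-exposure after a treatment-ending toxicity.

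Fifth, Section 8.1.5.1 already collects medical history, so a past myocarditis or hepatitis would ordinarily be recorded. That is fair; only its grade is not named.

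**Conclusion.** The gap is real and modest. No exclusion names a resolved severe immune-related event outside the lung, and the two criteria that might catch one are discretionary (43) or aimed at a different condition (24). It merits a cheap improvement to a design choice. The number of affected patients cannot be derived from the protocol; that it is small is an assumption.

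A reader might infer more than the documents support:

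- **That Table 14 shows past ALT/AST above 5 × ULN should bar entry.** Table 14 concerns on-study elevations attributable to either drug, and Section 6.6.6.3 calls it suggestions. The hepatitis example rests on Table 11.
- **That Part 1 dose finding is compromised.** A recurrence within 21 days could be a DLT under Table 8, and one more DLT can move Table 5, for example from 0/3 (escalate) to 1/3 (stay). Any DLT does the same, and Section 6.5.2 makes dose decisions by consensus on the whole of the safety data. This is a side effect, not the reason to act.
- **That any immune-related event which ended earlier therapy should exclude.** A patient taken off an earlier antibody for Grade 2 colitis or dermatitis would be barred, although Table 11 lets INCB099280 resume or continue after those events. In cohorts where prior therapy is mandatory, that would be a separate trade-off.

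**What to change.** Add one criterion to Section 5.2:

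*History, on prior anti-PD-(L)1 therapy, of immune-related myocarditis or pericarditis Grade 2 or higher (any grade if biopsy-proven), hepatitis Grade 3 or higher, or any other Grade 4 irAE. Exception: endocrinopathy controlled on stable hormone replacement.*

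This follows Table 11. Grade 4 colitis, dermatitis, nervous system and other immune-related events all end INCB099280 there, and Grade 4 nephritis does so when the drug is directly implicated. The Grade 4 endocrine rows only withhold it, hence the exception. Exclusions 7, 22, 24 and 43 can stay as they are.

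As a supporting detail, record the grade of any prior immune-related event on the screening eCRF so that the criterion can be verified.

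The cost is amendment wording and a screening field. Some pre-treated patients lose eligibility, and the trial gives up rechallenge data in them; the number is expected to be small but cannot be derived from the protocol.
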